### **11.5.4 Response Review**

All responses will be reviewed by the study co-investigator radiologist.

## **12. ADVERSE EVENT REPORTING REQUIREMENTS**

### **12.1 General**

This study will use the descriptions and grading scales found in the NCI Common Terminology Criteria for Adverse Events version 4.0 (CTCAE v 4.0) that is available at <http://ctep.cancer.gov/reporting/ctc.html>.

Information on all adverse events, whether reported by the participant, directly observed, or detected by physical examination, laboratory test or other means, will be collected, recorded, followed and reported as described in the following sections.

Participants should be instructed to report any serious post-study event(s) that might reasonably be related to participation in this study. The investigator should notify the IRB and any other applicable regulatory agency of any unanticipated death or adverse event occurring after a participant has discontinued or terminated study participation that may reasonably be related to the study.

## 12.2 Definitions

### 12.2.1 Adverse Event (AE)

An adverse event is any undesirable sign, symptom or medical condition or experience that develops or worsens in severity after starting the first dose of study treatment or any procedure specified in the protocol, even if the event is not considered to be related to the study.

Abnormal laboratory values or diagnostic test results constitute adverse events only if they induce clinical signs or symptoms or require treatment or further diagnostic tests.

### 12.2.2 Serious adverse event (SAE)

A serious adverse event is an undesirable sign, symptom, or medical condition which:

- ξ is fatal or life-threatening;
- ξ requires or prolongs inpatient hospitalization;
- ξ results in persistent or significant disability/incapacity;
- ξ constitutes a congenital anomaly or birth defect; or
- ξ jeopardizes the participant and requires medical or surgical intervention to prevent one of the outcomes listed above.

Events **not** considered to be serious adverse events are hospitalizations for:

- ξ routine treatment or monitoring of the studied indication, not associated with any deterioration in condition, or for elective procedures
- ξ elective or pre-planned treatment for a pre-existing condition that did not worsen
- ξ emergency outpatient treatment for an event not fulfilling the serious criteria outlined above and not resulting in inpatient admission
- ξ respite care

### 12.2.3 Expectedness

- ξ Expected: Expected adverse events are those that have been previously identified as resulting from administration of the agent. For the purposes of this study, an adverse event is considered expected when it appears in the current adverse event list, the Investigator's Brochure, the package insert or is included in the informed consent document as a potential risk.

- ξ Unexpected: An adverse event is considered unexpected when it varies in nature, intensity or frequency from information provided in the current adverse event list, the Investigator's Brochure, the package insert or when it is not included in the informed consent document as a potential risk

#### 12.2.4 Attribution

- Causality assessment is the determination of whether there is a reasonable possibility that the Pfizer product or blinded therapy caused or contributed to an AE. The Principal Investigator should provide a rationale and medical justification for this determination.
- This assessment is to be recorded on the IIR SAE Form (or other agreed reporting method) along with a description of the SAE that is sufficiently detailed to allow for complete medical assessment of the case and determination of possible causality.

Attribution will be assigned as follows:

- ξ Definite – The AE is clearly related to the study treatment.
- ξ Probable – The AE is likely related to the study treatment.
- ξ Possible – The AE may be related to the study treatment.
- ξ Unlikely - The AE is doubtfully related to the study treatment.
- ξ Unrelated - The AE is clearly NOT related to the study treatment.

#### 12.3 Potential Adverse Events

Signs and symptoms of disease progression are not considered AEs. The development of a new cancer should be regarded as an AE. New cancers are those that are not the primary reason for administration of study treatment and have been identified after inclusion of the patient into the clinical study.

Because patients are receiving standard treatments, which are not part of this study, their treating physician will be counseling them on the risk of their treatments, including the risk of SBRT. The procedures related to the study are phlebotomy, PET imaging (optional), SBRT, and CBI administration.

Phlebotomy can cause pain, bleeding, and rare needle site infection. PET imaging results in low dose radiation exposure (see Investigator's Brochure for details of dosimetry), which has an extremely small risk of causing a secondary cancer.

#### 12.4 Stereotactic Body Radiation Treatment

It is reasonable to extrapolate expected toxicity rates from the current experience and reported literature with SBRT. One significant toxicity is radiation pneumonitis, which can be manifested as fever, increased exertional dyspnea, pleuritic chest pain, and peritumoral infiltrate on chest imaging. It generally occurs between 1 to 3 months of completion of radiotherapy. The risk of grade 2-4 radiation pneumonitis is approximately 10-20% in patients treated with conventional large field radiotherapy and higher in patients treated with combined chemoradiotherapy. It is highly dependent on the volume of the lung treated to high dose and the mean lung dose.

Importantly SBRT has a significantly better tolerated with a limited side effect profile compared to conventional large field radiation. For example the rates of Radiation

Pneumonitis with SBRT have been reported as less than 5%. At this point, the incidence of RT pneumonitis from SBRT combined with immunotherapy for small pulmonary tumors is unknown. However, if the proposed radiation dose constraints are used the risk should be <10% with the proposed dose level.

Other toxicities commonly associated with such treatment includes colitis, diarrhea, hypophysitis, rash, arthritis, fatigue, nausea, vomiting, anorexia, and weight loss. Some of these symptoms could also be due to tumor progression. Clinical and radiographic assessments will be performed as indicated to identify all adverse effects, ascertain their etiology, and provide the most appropriate palliative measures. Complications will be graded according to the Common Toxicity Criteria, National Cancer Institute, version 4.0.

## 12.5 Reporting Procedures

### 12.5.1 General

An adverse event (AE) is defined as any untoward medical occurrence in a patient or clinical investigation subject following use of a Pfizer medication (or blinded therapy) or medical device (collectively, Pfizer product). There does NOT need to be a causal relationship between the event and the Pfizer product.

An SAE is any AE that:

- ξ Results in death
- ξ Is life-threatening (i.e., causes an immediate risk of death)
- ξ Requires inpatient hospitalization or prolongation of existing hospitalization
- ξ Results in persistent or significant disability or incapacity (i.e., substantial disruption of the ability to conduct normal life functions)
- ξ Results in a congenital anomaly or birth defect or that is considered to be: An important medical event

Adverse events will be recorded at each visit. If an adverse event requiring medical attention occurs between visits, this will be recorded as well. The variables to be recorded for each adverse event include, but are not limited to, onset, resolution, intensity, action taken, outcome, causality rating and whether it constitutes an SAE or not. The intensity of the adverse event should be captured using CTCAE criteria, version 4.0, when possible.

All AE or SAE will be captured on the appropriate study-specific case report forms or **IIR Serious Adverse Event Report Form**. Refer to the IIR SAE Manual INTERVENTIONAL IIRs Nov 2013 for additional details regarding AE reporting.

## 12.5.2 Required Reporting Times Frames to Pfizer, Principle Investigator, and Regulatory Authorities

The time frame for reporting an SAE to Pfizer is:

- ξ Immediately upon awareness, if the SAE is fatal or life-threatening (i.e., causes an immediate risk of death) —regardless of the extent of available information
- OR
- ξ Within 24 hours of first awareness of the SAE, if the SAE is not fatal or life threatening

These timeframes are applicable to all reportable SAEs

A report of an SAE, as provided on the IIR SAE Form (or other agreed reporting method) must contain at least the following four elements:

### 1. An identifiable subject(s)

There must be sufficient information that an SAE has been experienced by a specific individual.

Note: Patient names are NOT required and should not be reported.

### 2. Suspect product

The report must identify the suspect Pfizer product (i.e. the Pfizer product that the study subject received and that is the focus of the study).

### 3. SAE

The report must contain at least a description of an SAE (diagnosis or signs and symptoms) or an otherwise reportable event (i.e. exposure during pregnancy, exposure during breastfeeding and occupational exposure).

Notes:

- Do not report a procedure as an SAE, but instead report the SAE for which the procedure was indicated.
- Avoid recording “Death” as an SAE whenever possible. Report the cause of death as the SAE with “Resulted in death” checked as a seriousness criterion.
- In the case of a subject’s death, include a summary of autopsy findings, if available.

### 4. Identifiable reporting source

The report must contain information that clearly identifies the reporter, which establishes that there was firsthand knowledge of the identifiable subject.

It is important that information regarding an SAE be reported within the established timelines as described in the ‘Required Reporting Times Frames’ section above. If a report is delayed, then the reason for the delay should be clearly explained.

- Examples of reasons for delay:

- ξ Information missed due to clerical issues at the site
- ξ Correction of previously transmitted information

Serious adverse events, or a follow up to a serious adverse event, including death due to any cause other than progression of the cancer under study that occurs to any subject from the time study treatment initiation through 90 days following cessation of treatment, or the initiation of new anti-cancer therapy, requires expedited reporting as described below:

- A) The Study Chair and Site Principal Investigator must be notified within 24 hours of learning of any serious adverse events (SAEs).
- B) The Institutional Review Board (IRB) of each site must be notified by the site principal investigator according to their local policies.
- C) The UCSD Human Research Protections Program (HRPP) and Moores Cancer Center Data and Safety Monitoring Board (DSMB) must be notified within 10 business days of “any unanticipated problems involving risk to subjects or others” (UPR). The following events meet the definition of UPR:
  1. Any serious event (injuries, side effects, deaths or other problems), which in the opinion of the Principal Investigator was unanticipated, involved risk to subjects or others, and was possibly related to the research procedures.
  2. Any serious accidental or unintentional change to the IRB-approved protocol that alters the level of risk.
  3. Any deviation from the protocol taken without prior IRB review to eliminate apparent immediate hazard to a research subject.
  4. Any new information (e.g., publication, safety monitoring report, updated sponsor safety report), interim result or other finding that indicates an unexpected change to the risk/benefit ratio for the research.
  5. Any breach in confidentiality that may involve risk to the subject or others.
  6. Any complaint of a subject that indicates an unanticipated risk or that cannot be resolved by the Principal Investigator.
- D) The FDA must be notified by the Study Chair according to the following timelines:
  - Within 7 calendar days of any unexpected fatal or life-threatening adverse event with possible relationship to study drug, and
  - Within 15 calendar days of any event that is considered: 1) serious, 2) unexpected, and 3) at least possibly related to study participation.

### 12.5.3 Institutional Review Board

All adverse events and serious adverse events will be reported to the IRB per current institutional standards. If an adverse event requires modification of the informed consent, these modifications will be provided to the IRB with the report of the adverse event. If an adverse event requires modification to the study protocol, these modifications will be provided to the IRB as soon as is possible.

#### 12.5.4 **Exposure During Pregnancy, Breastfeeding and Occupational Exposure**

- ξ Exposure During Pregnancy occurs when a fetus (from pre-embryo to birth) may have been exposed at any time during pregnancy to a Pfizer product (or blinded therapy).
  
- ξ Exposure During Pregnancy is reportable to Pfizer regardless of whether there is an associated SAE. The specific details that need to be included in the report of an Exposure During Pregnancy depend on whether the exposure was maternal or paternal. The anticipated date of delivery should be included in the Narrative section of the report, for both maternal and paternal exposures. The Principal Investigator must then follow the subject throughout the pregnancy and is to notify Pfizer of the outcome as a follow-up to the initial Exposure During Pregnancy report.
  
- ξ If the outcome of the pregnancy meets any of the criteria for seriousness, report it to Pfizer as an SAE. To the extent known, provide information about the mother or the father and the pregnancy within the Narrative or other appropriate field of the agreed reporting method [**Use Exposure\_During\_Pregnancy\_(EDP)\_Supplemental\_Form**]
  
- ξ An exposure during breastfeeding occurs if an infant or child may have been exposed through breast milk to the Pfizer product during breastfeeding by a female taking the Pfizer product. Exposure during breastfeeding is reportable to Pfizer regardless of whether there is an associated SAE in the infant or child.
  
- ξ An occupational exposure is an exposure to a Pfizer product for human use as a result of one's occupation. An occupational exposure is reportable regardless of whether there is an associated SAE.

#### 12.5.5 **Follow-up Information**

When new, updated, or corrected information about a previously reported SAE is obtained, a follow-up report should be submitted to Pfizer on a new IIR SAE Report Form (or other agreed reporting method) that includes the data that are new or revised from the previous report. Follow-up information should never be added to a previously submitted report form. Ensure that any new events included on a follow-up report are marked as serious and a causality assessment is provided for each of them. Patients who experience grade IV toxicity will continue to be followed until toxicity resolution to Grade  $\leq 1$  or return to baseline.

#### 12.5.6 **Otherwise Reportable Events**

Certain types of events, as identified below, are reportable to Pfizer under the reporting processes and requirements for SAEs, even if there is no associated adverse event. These are considered “otherwise reportable events” and generally reflect circumstances that could lead to an increased risk of an adverse event. Like an SAE, an otherwise reportable event is to be reported to Pfizer within 24 hours of awareness on an IIR SAE Form (or other agreed reporting method) and followed up to determine outcome, including the

later occurrence of an associated SAE.

### **13. DATA AND SAFETY MONITORING PLAN**

A Data Monitoring Committee (DMC) will be established to provide oversight of safety and efficacy evaluation of the entire study and to provide advice to the sponsor regarding actions the committee deems necessary for the continuing protection of subjects. The DMC will be charged with assessing such actions in light of an acceptable benefit/risk profile for Avelumab + SBRT. The DMC will act in an advisory capacity to the sponsor and will monitor subject safety and evaluate the available efficacy data for the study. The DMC will meet at least every 6 months or more frequently as needed on an ad-hoc basis. Information regarding DMC membership, responsibilities, and procedures are detailed in the DMC charter. The DMC will be informed should a safety signal emerge and may convene an ad-hoc meeting on its own initiative. Ultimately, decisions regarding the study protocol will be made by the sponsor in conjunction with feedback from investigators and the DMC.

Patient safety will be monitored on an ongoing basis. Safety conference calls with investigators and representatives of the sponsor will be held as necessary. The DMC will review all available data (safety and efficacy) data at each meeting. At the conclusion of each DMC meeting the committee, will provide the sponsor with a recommendation to continue, modify or terminate the study protocol based upon their review.

All reportable anticipated and unanticipated protocol events/problems and amendments that are submitted to the IRB will also be reviewed by the DMC Chair (or designee) and QA manager.

### **14. REGULATORY CONSIDERATIONS**

#### **14.1 Protocol Review and Amendments**

Information regarding study conduct and progress will be reported to the Institutional Review Board (IRB) per the current institutional standards.

Any changes to the protocol will be made in the form of an amendment and must be approved by the IRB prior to implementation.

#### **14.2 Informed Consent**

The investigator (or his/her designee) will explain to each subject the nature of the study, its purpose, the procedures involved, the expected duration, the potential risks and benefits involved and any discomfort it may entail. Each subject will be informed that participation in the study is voluntary, that she may withdraw from the study at any time, and that withdrawal of consent will not affect her subsequent medical treatment or relationship with the treating physician(s) or institution. The informed consent will be given by means of a standard written statement, written in non-technical language, which will be IRB approved. The subject should read and consider the statement before signing

SBRT and Avelumab Protocol #161591

PI: [name].,Ph.D

November 8, 2018

and dating it, and will be given a copy of the document. No subject will enter the study or have study-specific procedures done before his/her informed consent has been obtained.

In accordance with the Health Information Portability and Accountability Act (HIPAA), the written informed consent document (or a separate document to be given in

conjunction with the consent document) will include a subject authorization to release medical information to the study sponsor and supporting agencies and/or allow these bodies, a regulatory authority, or Institutional Review Board access to subjects' medical information that includes all hospital records relevant to the study, including subjects' medical history.

### **14.3 Ethics and GCP**

This study will be carried out in compliance with the protocol and Good Clinical Practice, as described in:

1. ICH Harmonized Tripartite Guidelines for Good Clinical Practice 1996.
2. US 21 Code of Federal Regulations dealing with clinical studies (including parts 50 and 56 concerning informed consent and IRB regulations).
3. Declaration of Helsinki, concerning medical research in humans (Recommendations Guiding Physicians in Biomedical Research Involving Human Subjects, Helsinki 1964, amended Tokyo 1975, Venice 1983, Hong Kong 1989, Somerset West 1996).

The investigators agree to adhere to the instructions and procedures described in it and thereby to adhere to the principles of Good Clinical Practice that it conforms to.

## **15. STATISTICAL CONSIDERATIONS**

### **15.1 Endpoints**

#### **15.1.1 Primary Objectives**

Phase I: The Phase I primary endpoint is safety and tolerability as described in Section 3.1.1. Tolerability and safety of will be determined after all patients have completed six doses or have discontinued dosing prior to completing six doses. Safety analyses will be performed in all treated subjects. Descriptive statistics of safety will be presented using National Cancer Institute (NCI) Common Terminology Criteria for Adverse Events (CTCAE) version 4.0.

Phase II: The Phase II primary endpoint is to determine the relapse free survival rate at a median followup of 2 years in early stage NSCLC treated with definitive SBRT combined with 6 cycles of concurrent and adjuvant Avelumab.

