#### 6.5 Duration of Therapy

The patient will receive 4-5 fractions of SBRT radiation total administered every other day. The patient will receive Avelumab administered every 2 weeks for a total of 6 cycles. Thus the total duration of therapy is expected to last approximately 3 months.

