#### **15.2 Sample Size/Accrual Rate**

Phase I: The purpose of the Phase I part of this study is to evaluate the tolerability and safety profile SBRT combined with concurrent and adjuvant Avelumab at 10mg/kg. For this purpose, 12 subjects will be enrolled. Although the sample sizes are not based on statistical power considerations, data from these subjects will provide toxicity and dosing information on administration Avelumab in combination with SBRT in patients with early Stage NSCLC. The accrual rate is estimated at 3 patients per month.

Phase II: The primary endpoint will be relapse free survival (RFS) rate at median followup of 2 years. The accrual rate is estimated at 3 patients per month, and the patients will be

followed for up to 3 years. A total of 56 patients will be entered in the study accounting for a 10% dropout rate. This study would have 80% power to detect a 10% absolute improvement in RFS at 2 years from 80% to 90% using a one-sided t-test at significance level 0.10. RFS estimate at 2 years was based upon analysis of relevant literature[55-57].

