### 15.4 Analysis of Primary Objectives

Phase I: If no more than one-third of the subjects permanently discontinue study medication prior to completing six doses due to treatment related adverse events then this combination will be deemed as tolerable and return to the IRB, DMC, and Sponsor for further evaluation and approval prior to proceeding to the Phase II cohort.

If  $\geq 4$  patients in the Phase I cohort permanently discontinue study medication prior to completing six doses due to treatment related adverse events then we will suspend the study and return the study to the IRB and DSMB committees for further evaluation and recommendations.

Phase II: The primary efficacy analysis will be the relapse free survival (RFS) rate in patients with early Stage NSCLC receiving SBRT combined with concurrent and adjuvant Avelumab compared to SBRT alone historical controls. The analysis population includes all registered subjects who have received SBRT and at least 2 cycles of Avelumab.

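### Section 15.4 suspends the study at four related discontinuations in Phase I but does not say when the count is read; the only stated time is after Phase I dosing has ended

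*Combined protocol and SAP*

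**What the plan says.** - **Timing.** Section 15.1.1 says that Phase I tolerability and safety "will be determined after all patients have completed six doses or have discontinued dosing prior to completing six doses".
- **Tolerable.** Section 15.4, first paragraph, calls the combination tolerable, subject to IRB, DMC and sponsor approval before Phase II: "If no more than one-third of the subjects permanently discontinue study medication prior to completing six doses due to treatment related adverse events".
- **Suspend.** Section 15.4, second paragraph, applies when 4 or more of the Phase I patients stop avelumab for good, before their sixth dose, because of related events. The stated consequence is to "suspend the study and return the study to the IRB and DSMB committees for further evaluation and recommendations". It contains no timing words.
- **Cohort and schedule.** Section 15.2: "For this purpose, 12 subjects will be enrolled" and "The accrual rate is estimated at 3 patients per month". Section 6.5: "The patient will receive Avelumab administered every 2 weeks for a total of 6 cycles".
- **Run-in.** Section 15.3 observes the first six patients for 30 days after radiation and goes on to 12 only if no more than 3 of them have a related event of grade 3 or higher.
- **General oversight.** Section 12.5.2 requires SAEs to reach the Study Chair within 24 hours. Section 13 provides ongoing safety monitoring and DMC meetings at least every 6 months, with ad hoc meetings possible.

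**The concern.** A count of permanent discontinuations cannot fall. Once the fourth occurs, the suspension condition is met whatever happens to the remaining patients. If the count is read only at the time given in 15.1.1, patients can still be enrolled and dosed after the plan's own limit has been reached. Suspension would then hold back only Phase II, which already needs separate approval even after a favourable result.

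The run-in does not cover the same ground:

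- It stops at patient 6, so patients 7 to 12 have no other cohort-level count.
- It counts only grade 3 or higher events, whereas 8.1 and 8.2 can require permanent discontinuation for persistent or repeated grade 2 events.
- Its window is 30 days after radiation, whereas 12.4 places radiation pneumonitis mostly at 1 to 3 months after radiotherapy.

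**Working it through.** The plan gives no error rate or power for the Phase I rule (15.2 says the sample size is not power-based), so there is no stated figure to reproduce.

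**1. When an end-of-cohort read would fall.**
- Accrual of 3 per month is one patient every 365.25/36 = 10.1 days, so patient 6 starts at about day 5 × 10.1 = 51.
- SBRT starts 3–10 days after dose 1 (6.3.2). Four or five fractions every other day (6.5) take 6–8 days, so SBRT ends at day 9–18 of a patient's treatment. Adding 30 days, the run-in window closes at day 39–48, after 3–4 of the 6 doses.
- The run-in therefore reads at about study day 90–99. Patient 12 starts 5 × 10.1 days later, at about day 140–149, and receives dose 6 (70 days after dose 1) at about day 210–219.

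An end-of-cohort read comes at roughly 7 months, with no Phase I dose left to give.

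**2. How often the limit is reached.** With X the number discontinuing among 12 and p the true rate, P(X ≥ 4) = 1 − Σ(x = 0 to 3) C(12,x) pˣ(1−p)¹²⁻ˣ. At p = 0.20 this is 1 − (0.0687 + 0.2062 + 0.2835 + 0.2362) = 0.205. At 12% it is 0.046.

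**3. What follows the fourth discontinuation.** Simulation, 40,000 trials per rate. Assumptions that are not in the documents: the true rate, random (Poisson) accrual at 3 per month, patient 7 starting 44 days after patient 6 (14 days to the end of SBRT plus 30), stopping equally likely after any of doses 1–5, and no trial stopped under 15.3 or by the DMC. Averages are over trials that reach four.

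| Assumed rate | P(X ≥ 4) | Further patients enrolled | Further doses | Days from fourth discontinuation to last dose or stop |
|---|---|---|---|---|
| 20% | 0.205 | 0.7 | 11 | 48 |
| 33% | 0.607 | 1.3 | 13 | 60 |
| 50% | 0.927 | 2.4 | 18 | 80 |
| 60% | 0.985 | 3.3 | 20 | 94 |

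Over all trials the figures are smaller. At 33% they are 0.607 × 1.3 = 0.8 patients and 0.607 × 13 = 8 doses; at 20%, 0.205 × 0.7 = 0.1 patients and 0.205 × 11 = 2 doses.

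**4. Sensitivity.** A second model used even accrual, stopping uniform over the 70 dosing days and SBRT finished at day 16. At 30 / 40 / 50% it gives 1.4 / 2.0 / 2.9 patients not yet enrolled, 14 / 17 / 19 doses remaining and a lead of 63 / 73 / 86 days. The order of magnitude does not depend on these choices.

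**5. How much the run-in would catch.** If run-in events occurred at the same rate as discontinuations (an assumption), P(4 or more of 6) = 0.017 / 0.100 / 0.344 / 0.544 at 20 / 33 / 50 / 60%. It would catch little at the lower rates. At the higher rates it would remove a real share of the exposure in the table.

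**6. The overlap at four.** One-third of 12 is exactly 4, so 4 of 12 satisfies both sentences of 15.4. P(X = 4) = 0.133 at 20% and 0.238 at 33%. As a share of trials reaching four, that is 0.133/0.205 = 65% and 0.238/0.607 = 39%.

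**The case against.** The strongest reply is that no section says the count is read only at the end. The sentence in 15.1.1 fits the tolerability declaration in 15.4's first paragraph. The suspension paragraph stands apart, has no timing words, and can be read as acting as soon as the fourth discontinuation occurs. A reader might infer that the rule is definitely read only after all 12 patients and so cannot protect any Phase I patient; the text does not establish that. What stands against the reply is that 15.1.1 gives the only read time, both paragraphs of 15.4 are framed around completing six doses, and the plan puts its interim check in a separate section. The end-of-cohort reading is therefore the natural one, and the text does not exclude it.

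A reader might also infer that a regimen with four discontinuations has certainly failed, so that reading the count earlier leaves every pass/fail probability unchanged. That does not hold either: at exactly 4 of 12 the tolerability sentence is still met, so the outcome is undefined until 15.4 is reconciled.

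Other protection is real. The run-in gates patients 7–12, 8.1 and 8.2 set individual stopping rules, SAEs are reported quickly, and the DMC can meet ad hoc. But individual rules protect the patient who has the event, non-serious discontinuations are outside SAE reporting, and nothing directs the DMC to this count. Meetings at least every 6 months could mean a single scheduled meeting in a dosing period of about 7 months.

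The rates are also assumed. The nearest figures in the plan are lower: 12% drug-related grade 3 or higher events with avelumab alone (4.2) and an expected pneumonitis risk below 10% (12.4). Neither is a discontinuation rate for the combination, but at 12% the limit would be reached in only about 5% of trials.

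**Conclusion.** The point holds as an unstated read time, not as a proven end-only read. If the count is applied at the time given in 15.1.1, suspension comes too late to spare any Phase I patient a dose, although it would still hold Phase II. In trials that reach four discontinuations, the avoidable exposure is roughly 1 to 3 further patients and 11 to 20 further doses, over 48 to 94 days, at assumed rates of 20–60%. These figures rest on the assumed rates and stopping times and ignore any intervention under 15.3 or by the DMC, so they are upper-end estimates at the higher rates. The conflict at exactly 4 of 12 is a direct contradiction within 15.4 and needs no assumption. Both should be corrected: the read time decides whether the suspension rule works while Phase I patients are on treatment.

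**What to change.** Reconcile 15.1.1 with 15.4. State that the existing suspension count is tracked as discontinuations occur, from the first Phase I patient, and that 15.4's suspension and committee review take effect when it is met. Keep the end-of-cohort read in 15.1.1 for the descriptive safety summary and the tolerability declaration. In the same edit, reconcile 15.4's two sentences so that exactly 4 of 12 leads to one outcome; which one is for the sponsor and the committees to decide.

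The cost is a sentence or two of text and no additional patients. The coordinating centre must learn of every related permanent discontinuation promptly, including non-serious ones that SAE reporting would miss, and accrual may pause earlier than it would under an end-of-cohort read.
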